Figure 2: Results from previous coverage survey in 2014. Chikwawa, Rumphi and Salima were selected to be revisited during the 2016 coverage survey.

2016

The 2016 coverage survey was conducted in six districts. One district in each region was purposively selected (Chikwawa, Rumphi and Salima), as these were previously surveyed during the 2014 coverage survey and results had demonstrated a need for improvement. In addition, three other districts randomly selected, one from each of the same three region were also surveyed Mchinji, Karonga and Neno districts.

Overall, the surveyed coverage was above the WHO recommended coverage of 75% of SAC in 5 of 6 districts surveyed. When adjusting for population size Mchinji fell below the 75% coverage for SAC. Reported coverage was not significantly different from surveyed coverage in four of the districts for ALB and PZQ, reported coverage was significantly different than surveyed coverage in the remaining two remaining districts, one higher and one lower than reported.

This survey also found there was a significant difference in the coverage between those who do and do not attend school for all districts and there was no significant difference in coverage between the genders. The full protocol and recommendations report can be found here:

https://share.imperial.ac.uk/fom/IDE/SCI/The%20Hub/MWI_2016CoverageSurveyProtocol_EN.docx

https://share.imperial.ac.uk/fom/IDE/SCI/The%20Hub/MWI_Coverage_Recommendations_Report_ EN.docx

Details of the MDA in Malawi 2017

The MDA took place between the 10-14th July 2017. The MDA was conducted in every district in Malawi except the islands of Likoma. SAC were targeted in every district and treatment predominantly delivered in schools for the SAC, as well community-based treatments for children who do not attend school and adults in the high-risk areas.

In addition to the standard radio campaigns and social mobilisation that are conducted annually, the MoH was supported by SCI and Development Media International (DMI) with the delivery of an enhanced media plan which involved 3×1 minute radio clips which started with the Doctor testimonial (25/6/17 - 1/7/17), followed by the Mother testimonial (2/7/17 - 8/7/17) and lastly the clip "Give me my breakfast" Appendix F. Each of the clips was broadcast 70 times (7 times adjacent to the News), across 9 radio stations and in 4 languages: Chichewa, Lhomwe, Tumbuka and Yao.

Coverage targets for MDA in 2017

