Survey Objective (SO) 1. To measure validated treatment coverage of PZQ and ALB in SAC, and adults relative to coverage targets

SO 2. To compare reported and validated coverage of PZQ and ALB for SAC and adults

SO 3. To assess coverage in SAC and adults disaggregated by gender

SO 4. To assess coverage in SAC disaggregated by school attendance

SO 5. Collect information on why targeted eligible individuals did not receive or accept treatment

- SO 6. To assess the impact of radio campaigns on improving knowledge about schistosomiasis
- SO 7. To assess whether radio campaigns improved attendance/coverage of treatment with PZQ and ALB

Where validated coverage rate is defined as:

Total number of interviewed individuals that ingested the target drug Total number of interviewed individuals * 100 %

Note that people interviewed but with missing information on whether they ingested the drug will be assumed to have **not** taken the drug for the purposes of calculating validated coverage.

Study Design

Overview

The coverage survey will take place in nine implementation units (IUs) known as the district. Each IU will be considered separately. Within each IU, the survey will be household (HH) based in randomly selected villages. See Appendix D for a detailed explanation of the statistical approach to the coverage survey.

Survey team

Interviewers must not have been involved in any previous activities related to the NTD programme, specifically the MDA, to ensure that they remain unbiased.

Selection of enumerators will be done by the Programme Managers, ensuring that none of the interviewers were involved with the MDA in July 2017. The majority of interviewers have experience in coverage surveys, but everyone will attend compulsory training to ensure standardisation of knowledge and ability to carry out coverage surveys. Training will include teaching about schistosomiasis and soil transmitted helminth infections as well as familiarisation with the health questionnaires and the phones that the information will be stored on.

Although programme managers will not take part in any of the individual interviews in interviewee households, they will facilitate in the training and logistics of the survey as well as support the teams of enumerators if problems arise.

See Appendix A for more details of the survey teams and logistics.

Timing of survey

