Mchinji	Surveyed Previously	
Rumphi	Surveyed Previously	
Ntcheu	Not surveyed previously	
Dedza	Not surveyed previously	Yes
Chitipa	Not surveyed previously	

Number of villages and households to survey within each IU

Sample size calculations indicated that 17 villages per IU, and 15 HHs per village are required to obtain 9% precision on the coverage of SAC and adults within each district. As the MDA was community-wide, two adults will be randomly sampled, and to capture more information about school attendance rates, all eligible children within a HH will be interviewed. See Appendix D for full details of sample size calculations.

Selection of villages to survey within each IU

A list of all traditional areas (TAs), and all their villages, within the selected districts were collected from the district health offices. The list of all TAs and their villages will ensure all villages have the opportunity to be selected. Each village was allocated a number and was then randomly selected by the in-country team using a random number generator until 18 villages per district were selected. The sample size calculation requires 17 villages, for logistical purposes 18 villages have been selected so that each team will visit 6 villages per district.

A short list of 'reserve villages' was provided, such that if a selected village cannot be visited for security or other unpredictable reasons, it can be replaced with another in the same district. See Appendix B: Coverage Survey Interviewer Manual for more details. Appendix E has a list of all selected villages and reserves

Selection of households to survey within each village

HH selection will be performed on site. Selection will be random, with the methodology dependent on whether HHs lists are available (see data collection protocol). If lists are not available HH selection will by the modified random walk procedure (please see data collection protocol).

Although ideally the survey would include nomadic populations and transient communities, because this is a HH-based survey, those without a fixed residence at the site selected for the coverage survey will not be included in the survey target population.

Selection of individuals to survey within each household

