If people in the selected home refuse to participate, try to encourage participation. If they still refuse, indicate this on the survey form, and count this HH as one of the HHs visited, indicate this on the survey form. **DO NOT replace the house with another HH**.

If no-one is at home in the selected HH, return later in the day. If, again, nobody is at home, indicate this on the survey form in the "Household questions" section, and count this HH as one of the HHs visited. **DO NOT** replace the HH with another one⁵.

If there are no eligible individuals for interview in the HH (e.g. no SAC live at the address, or all HH members moved in after the drug distribution), note this on the survey form, do not ask the questions, **but replace the HH with the next HH in the direction of travel with any eligible interviewee.**

Selecting individuals within a household

- If the head of the HH agrees to participate, proceed with the interview.
- Two adults and all school-aged children (SAC) within each HH will be randomly selected for interview.
- SAC is all children aged 5 -14 years
- Adults is all people aged 15 or over

The steps to take for interviewing SAC within a HH are:

- 1. Write the name of each SAC (i.e. all children aged 5 -14) in the HH on a separate piece of paper. Include all SAC living in the HH, even if they are not in the HH at the time.
- 2. Begin interviewing the children who are available for interview

⁵ If this happens for many households (e.g. frequently >2 households/village) in several villages, the supervisors should discuss with the study co-ordinator to consider increasing the number of households to randomly select per village.

3. If a selected individual cannot be interviewed, record who they are and please see below.

The steps to take for interviewing adults within a HH are:

- Write the name of each adult (i.e. all individuals 15 or over) in the HH on a separate piece of paper.
 Include all adults living in the HH, even if they are not in the HH at the time.
- 2. Fold up the pieces of paper and put into a container
- 3. Pick out two pieces of paper
- 4. Interview the adults whose names are on the paper
- 5. If a selected individual cannot be interviewed, please see below

What to do if an individual cannot be interviewed

- If an individual (SAC or adult) cannot be interviewed then return later to try to interview them.

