APPENDIX C: Data Collection Forms

Village Questionnaire

Cov	erage Survey - Village Questionnaire To be answered by the	ne interviewee
1	Date (DD/MM/YYYY)	
2	Interviewer Name	
3	GPS South on Arrival	
4	GPS East on Arrival	
5	District name (of implementation unit)	
6	TA name	
7	Village name	
8	What is the position in the village of the person being interviewed? (ENTER CODE)	
9	What is the total population of the village?	
10	What is the number of households in the village (interviewee to estimate if not known)	
11	Source of population data? (ENTER CODE)	
12	When was the mass treatment for schistosomiasis carried out? (month/year)	
13	How was the mass treatment provided in the village? (ENTER CODE)	
14	Did this treatment include adults?	□ Yes □ No
15	If the treatment was community based, how was treatment in the village carried out? (ENTER CODE)	
	To be answered by the interviewer	
16	Method of random sampling of households	Random selection from household listBottle spinning method
17	Notes about village interview	

8. Interviewee position?	11. Source of population data	13 How was the MDA
1. Village chief	1. Village register	treatment provided in the
2. Village deputy chief	2. Election register	village??
3. School head teacher	3. LF register	1. No MDA treatment was
	4. Malaria register	carried out
	5. Onchocerciasis register	2. School-based treatment
	6. General health register	3. Community-based
	7. Other (please specify)	treatment
		4. Both school-based and
		community-based
		treatment
		5. Do not know
15. If treatment was		
community based, how was		
treatment in the village		
carried out?		
1. Door to door		
2. At the house of the village		
head		
3. Central point in the village		
4. Local health centre		
5. At the village school		
6. Other		
7. Do not know		

Household Questionnaire

	Coverage Survey – Household Form To be an	nswered by the interviewer
7	What number house is this for you in the village?	
	(Enter one number)	
8a	Was this house interviewed?	D No
	(Tick one box)	Yes on first visit
		Yes on second visit
8b	If household not interviewed: Reason why	
	household not interviewed	
	(Tick one box)	
		Household not found or destroyed
		L Other
8c	If household not interviewed and reason 'other'	
	Reason not interviewed: other	
0	(Enter reason)	
9	Consent form signed by Head of House?	No: stop interview
	(Tick one box)	L Yes
	To be answered by the interviewee Household head	d or other adult
10	How many people live in this household?	

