coverage will then be calculable, assuming that the implementation units to be surveyed were randomly selected and a sufficient number (>15) were surveyed.

Selection of primary sampling units

Selection of primary sampling units is conducted by an SCI biostatistician. There are two main options when selecting PSUs to survey:

- 1. PSUs are selected from a list of all PSUs within the implementation unit, with no reference to population size. In this instance, every PSU has an equal probability of being selected and consequently HHs in small PSUs are more likely to be selected than HHs in large PSUs due the same number of individuals being interviewed in each PSU. This selection method is most commonly used when population sizes of the primary sampling units are not known. Analyses of coverage rates and associated 95% confidence intervals are be performed with and without adjustment for PSU size, collected as part of the survey.
- 2. PSUs are selected from a list of all PSUs within the implementation unit, with probability proportional to population size. In this instance, larger PSU's have a higher probability of being selected that smaller PSUs, leading to an equal probability of each individual in the implementation unit being selected. Analysis therefore does not require any adjustment for population size. Selection is performed without replacement to guard against the possibility of especially large PSUs being selected multiple times.

Sampling of individuals within a HH

Our standard protocol is for two SAC and two adults (if eligible for treatment) to be interviewed in each HH. Much of the differences in whether or not people received treatment is often between HHs rather than between individuals within a HH. If we were to interview everybody in the same HH then if particularly large HHs were surveyed the interview process could take a very long time meaning either that the teams would have to stay in the villages longer, or reduce the number of houses visited within some villages, neither of which is optimal. We believe that this method will not induce any biases as long as the protocol is followed of randomly selecting from the list of all eligible individuals in the HH.

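### Adult coverage is divided by every adult interviewed in a district, although community treatment and the 75% target were for at-risk adults; in partly targeted districts SO1 and SO2 will be biased downward

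*Protocol*

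**What the plan says.** **Who was treated.** Under Details of the MDA in Malawi 2017, children were treated mainly in schools, "as well community-based treatments for children who do not attend school and adults in the high-risk areas". Treatment History says the same of adults and adds that high-risk areas can sometimes be a whole district. The table under Coverage targets for MDA in 2017 sets >75% for at-risk adults, defined at implementation-unit or sub-implementation-unit level.

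**Who is sampled.** The section on the number of villages and households gives a different premise: "As the MDA was community-wide, two adults will be randomly sampled". Villages are drawn at random from all villages in the district, without stratifying by risk. In Appendix B, "Adults is all people aged 15 or over", and every such person in the household goes into the draw. Appendix D gives the general approach as "Our standard protocol is for two SAC and two adults (if eligible for treatment) to be interviewed in each HH"; the Malawi manual does not carry over the condition in brackets.

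**How coverage is calculated.** Study Objectives defines validated coverage as the ratio "Total number of interviewed individuals that ingested the target drug Total number of interviewed individuals * 100". It adds that "people interviewed but with missing information on whether they ingested the drug will be assumed to have" not taken the drug. SO1 compares adult coverage with the target, and SO2 compares it with reported coverage. The reported tables divide by persons registered at school or in the community.

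**What could separate the groups.** Village Questionnaire item 14 asks "Did this treatment include adults". Neither the coverage definition nor the Data collection and analysis section uses the answer.

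**The concern.** The target refers to at-risk adults, the reported figure to registered adults, and the validated figure to all adults in randomly drawn villages. These three populations coincide only if the whole district was targeted. Elsewhere, adults who were never meant to be treated through the community campaign enter the denominator, mostly as untreated.

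A district that reached nearly all its targeted adults could then appear to miss 75% under SO1 and to over-report under SO2. Detecting over-reporting is a stated purpose of these surveys, so the adult parts of two objectives could give misleading conclusions about programme performance.

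**Working it through.** **1. The plan's own sample size.** Inputs from Appendix D: coverage 50%, margin 9 points, ICC 0.1, 24 individuals per village, 95% confidence.
- Simple random sample: 1.96² × 0.25 / 0.09² = 118.6.
- Design effect: 1 + (24 − 1) × 0.1 = 3.3.
- Required n: 118.6 × 3.3 = 391, as stated. 391 / 24 = 16.3, rounded up to 17 villages. 15 households × 2 × 0.80 = 24 per village.

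The figure reproduces and is not in dispute. It assumes that all sampled adults count.

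**2. Direction of the bias.** Let f be the share of adults in targeted areas, C_t their coverage, and C_n the coverage of other adults.

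All-adult coverage = f × C_t + (1 − f) × C_n.

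This is below C_t whenever f < 1 and C_n < C_t. Take C_t = 87%, the national community adult praziquantel figure: (836,477 + 1,034,036) / (936,904 + 1,208,422) = 87.2%. With C_n = 0, f = 0.75, 0.50 and 0.25 give 65%, 44% and 22%. With C_t between 83% and 89%, coverage drops below 75% once f is under about 85-90%.

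**3. Illustration from the reported counts.** The protocol gives neither f nor the adult population. Two assumptions are therefore needed: registered adults stand in for targeted adults, and the number of adults per registered school-aged child (SAC) is set at 1.0 or 1.5. Counts are school plus community, praziquantel.

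| District | Adults registered | Adults treated | SAC registered | Registered adults per SAC | Treated / registered | Treated / all adults, ratio 1.0 | Ratio 1.5 |
|---|---|---|---|---|---|---|---|
| Mchinji | 35,329 | 30,597 | 160,383 | 0.22 | 87% | 19% | 13% |
| Ntcheu | 76,683 | 63,991 | 178,052 | 0.43 | 83% | 36% | 24% |
| Dedza | 115,458 | 102,181 | 272,884 | 0.42 | 89% | 37% | 25% |
| Karonga | 53,987 | 46,708 | 103,968 | 0.52 | 87% | 45% | 30% |
| Rumphi | 34,647 | 30,258 | 60,799 | 0.57 | 87% | 50% | 33% |
| Salima | 101,978 | 88,514 | 138,798 | 0.73 | 87% | 64% | 43% |

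Chitipa has no age split.

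**4. Sensitivity to the base.** School and community child registrations may overlap. With school-registered children only, Salima at 1.0 adult per child becomes 88,514 / 100,661 = 88%, above 75%. Scaling that base up for the 91% school attendance reported from the 2012 survey gives 88,514 / (100,661 / 0.91) = 80%. The other five districts stay below 75% at 1.0 on the school-only base.

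**5. Albendazole.** Reported community adult coverage is already (12,382 + 15,980) / 80,464 = 35% in Dedza and (6,809 + 6,990) / 26,535 = 52% in Rumphi.

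**6. Adult precision on a targeted denominator.** Margin = 1.96 × √(0.25 × 3.3 / (24k)) for k qualifying villages: ±14.8 points for 6, ±12.1 for 9 and ±10.5 for 12. All 17 villages would give ±8.8.

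**The case against.** A reader might infer that every surveyed district will falsely miss 75%, or that none could reach it. The protocol does not support that.

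- High-risk areas may be whole districts. Where that is so, the stated formula is right.
- Registered is not the same as targeted. Few registered adults may mean narrow targeting, or poor registration of adults who were targeted. In the second case a low survey result is a true finding. Registration is also imperfect: the national community praziquantel table shows 600,837 girls treated of 583,686 registered (103%).
- Adults per child is an assumption, and Salima passes 75% on one plausible base.
- People aged 15 and over were also registered at school: 17-42% of registered adults in the six districts. It is therefore too strict to say that only adults in high-risk areas were offered treatment.
- An albendazole miss in Dedza or Rumphi would be exaggerated rather than false.

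These points limit the size and certainty of the bias, but not its direction in a partly targeted district.

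It can also be said that Appendix D's eligibility condition is not listed among the deviations, that item 14 is collected, and that an analysis plan not available here may restrict the population. But Study Objectives states the denominator outright, Appendix B lists everyone aged 15 or over, and eligibility is not tied to village targeting. A later restriction would have to override the protocol's own definition.

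**Conclusion.** The point holds for the adult parts of SO1 and SO2. The protocol contradicts itself on who was targeted, and its coverage formula follows the wider reading while its target follows the narrower one. In any district only partly targeted, adult coverage is biased downward, provided that adults outside the targeted areas were treated less often.

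The size is unknown because the targeted share is not given. The illustrative gap, 83-89% against 19-64% or 13-43%, rests on accurate reports, on registered adults approximating targeted adults, and on the assumed adult-to-child ratio. It shows that the choice of denominator can decide the conclusion; it does not predict any district's result. Estimates for school-aged children are not affected.

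**What to change.** 1. Reconcile Treatment History, Details of the MDA, Coverage targets, the village and household numbers section, Appendix B and Appendix D on which adults were targeted in July 2017.
2. Define the SO1 and SO2 adult denominator as interviewed adults in areas targeted for adult treatment in that round. Take the areas from the district or Ministry categorisation, fixed independently of the survey responses.
3. Use item 14 only as a sensitivity check. It records whether treatment included adults, so a targeted village where adult distribution failed could answer no, leave the denominator and inflate coverage.
4. State how people aged 15 and over treated at school are handled.
5. Report all-adult district coverage separately, without the 75% benchmark, and compare with reported adult coverage only on the same areas.
6. Replace the 9-point precision stated for adults with the margin for the number of qualifying villages (step 6 of the working).

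The cost is protocol wording, an analysis rule, and obtaining the list of targeted areas. The list may take effort: the protocol says only that districts were asked in 2014 to begin categorising, and does not show that a 2017 village-level list exists. No new questionnaire item is needed. The price is wider adult intervals where few villages qualify.

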APPENDIX A: Field team planning manual

Survey team composition

Include a brief description of the survey teams: The participants were identified by the Malawi program manager as people with skills and experience relevant for the activity. The backgrounds from the participants ranged from IT Graduates, retired teachers to experienced Nurses from within the MoH.

Survey teams will be made up of students and people known to the program with interview skills but had no part in the MDA.

There will be 6 teams made up of 1 team leader, 3 interviewers and a driver.

The survey will take 5 weeks to complete all districts working Monday – Saturday each week.

Survey team training

Training for the survey will be conducted by the SCI PM, MoH PM with additional input from other Program staff. Below are links to the various training materials that will be used. Each interviewer will be provided with an Interviewer manual and cheat sheet for using the phones.

The questionnaire will be translated prior to the training and will be reviewed during the training to ensure they are fully understood. Each team will be provided with the same dose pole that was used during each distribution (MDA), samples of each of the drugs that were provided, and examples of the posters and leaflets used during social mobilization. These will act as visual cues to the individuals in each HH.

Training Material

Agenda:

https://imperiallondon.sharepoint.com/sites/fom/SCI/The%20Hub/MWI_Coverage%20Survey%20Training% 20Agenda_OCT%202017.docx

Schisto Overview:

https://imperiallondon.sharepoint.com/sites/fom/SCI/The%20Hub/GLO_Schisto%20Program%20Overview% 20for%20Coverage%20Survey%20Training.pptx

Coverage Survey Overview:

https://imperiallondon.sharepoint.com/sites/fom/SCI/The%20Hub/GLO_PP_Coverage%20Survey%20Trainin g%20Template.pptx

Household Selection Exercise: https://imperiallondon.sharepoint.com/sites/fom/SCI/The%20Hub/MDG-%20HH%20selection%20exercise.pptx

Phone Use:

https://imperiallondon.sharepoint.com/sites/fom/SCI/The%20Hub/TOOL_Coverage_SurveyCTO_Cheat_She et_EN.docx

Practice Scenarios:

https://imperiallondon.sharepoint.com/sites/fom/SCI/The%20Hub/GLO_Coverage%20Survey%20Training%2 OPractice%20Household%20Scenarios_EN.docx

Coverage Manual:

https://imperiallondon.sharepoint.com/sites/fom/SCI/The%20Hub/MWI%20Interviewer%20Manual%20201 7.docx?d=w9fd6a56081c14123b115a778483f6a84&csf=1

Timetable of activities

https://imperiallondon.sharepoint.com/sites/fom/SCI/The%20Hub/MWI_Coverage_Survey_Planning_2017.x lsx

Roles and responsibilities

The survey team will include the following main members:

Survey Coordinator

The NTD focal point (or other relevant national NTD control programme staff) will be the survey coordinator. The primary duties of the survey coordinator are:

- Together with the SCI program manager and biostatistician, adapt and finalise the survey protocol, including the questionnaire
- o If necessary, arrange translation and back translation of questionnaire in local languages
- o Together with the SCI program manager, identify the survey team
- Together with the SCI program manager, organise the survey logistics
- \circ ~ Together with the SCI program manager, train the survey team
- Together with the SCI program manager, oversee the data entry (paper or mobile-based).
- Lead one of the teams

SCI Program Advisor

The primary duties of the SCI program manager are to:

- o Obtain necessary ethical approvals (with the Ministry of Health)
- Adapt and finalise the survey protocol, including the questionnaire (with survey coordinator and SCI biostatistician)
- Obtain SCI sign-off of protocol
- o Together with survey coordinator, identify the survey team
- o Together with survey coordinator, organise survey logistics
- o Together with survey coordinator, train and supervise the survey team
- Together with survey coordinator, oversee the data entry
- \circ $\;$ Together with survey coordinator, write the final survey report

Team Leader

A team leader should be identified for each field team. The primary duties of the team leader are to:

- o Contact local authorities in the survey area to advise them about the study
- o Lead the selection of HHs within a village
- o Ensure strict adherence to the survey protocol
- Provide the survey teams with necessary materials for daily activities
- Review surveys for accuracy and completeness after each village is done.
- Review collected data (and eventual upload of data if mobile-based) at the end of each day
- o Manage daily logistics
- Lead a daily debrief with the team
- Provide the field report

Interviewers

The primary duties of the interviewers are to:

- Conduct interviews according to protocol and entering data (paper or mobile-based)
- Report any issues or concerns to the team leader as they occur

The team members must have the following competencies:

 \circ Understanding of the sampling protocol and the necessity of protocol compliance

- S/he does not need specific skills besides those that should be acquired during the survey training. If such a person is not available at the district level, he/she can be recruited from the national or regional level. In such cases, this person can administer surveys throughout the country as part of a national survey team.
- **Proficiency in the local language as well as general knowledge of the district** If possible, the team members should have some experience interviewing people.

Local Guide

Often, in each selected village, the team will be accompanied by a local guide. The local guide can help familiarize surveyors with the selected cluster (i.e. identifying village boundaries or included HHs), and introduce the survey team to local authorities and HH members if necessary. However, the local guide should not be involved with the HH selection or interview process. The local guide should not have been involved in the drug distribution.

Drivers

Due to the nature of cluster surveys, drivers play a vital role in the success of the survey by helping the survey team navigate between clusters. Preferably, drivers should be familiar with the survey area. The number of drivers needed will vary based on the local situation.

Data Entry Personnel

The data entry personnel must be knowledgeable of data management and data entry.

SCI Biostatistician

The primary duties of the SCI biostatistician are to:

- Together with the survey coordinator and SCI program manager, adapt and finalise the survey protocol, including the questionnaire
- o Determine the sampling strategy and number of villages and HHs to sample
- Select the villages to sample
- \circ Clean the data
- \circ $\,$ Analyse the data and produce graphs and tables with SCI PM $\,$
- $\circ\quad$ Write the data cleaning notes in the report

